7.4.2. Other Secondary Efficacy and Exploratory Endpoints

The following describes the analysis methods for other secondary efficacy endpoints and exploratory endpoints. There are three types of analyses corresponding to the three types of endpoints (time-to-event, continuous and binary) (see [Appendix 1](#) for details).

Time-to-Event Endpoint

For time to achieving an MBL volume of < 80 mL AND at least a 50% reduction from Baseline MBL volume (as an event), time to event will be defined as weeks from date of first dose of study drug to response (event) based on the MBL volume as assessed by the alkaline hematin method. The missing data handling rules described in Section [7.3.5](#) for deriving responder status at Week 24/EOT will be applied similarly at Weeks 8, 12, 16, and 20. Patients without an event will be censored at the last assessment date prior to the last dose of the study drug.

Kaplan-Meier methods will be used to describe the time to event distributions. A log-rank test stratified by the randomization stratification factors using the proportional hazard model (p-value from score test) will be used to compare relugolix + E2/NETA to placebo. Randomization stratification factors will be used to stratify inferential testing.

Continuous Endpoints

For endpoints evaluating the change (absolute or percent change) from Baseline to Week 24, treatment comparisons will be performed using a mixed model repeated measures approach with treatment, randomization stratification factors, visit, and treatment by visit interactions included as fixed effects. The Baseline value will be included as a covariate, and an unstructured variance-covariance matrix will be assumed. Calculation of the dependent variable (change from Baseline) for each patient at each visit will be calculated based on the visit windows specified in Section [4.3.5](#). Based on this model, the least squares mean at Week 24 will be compared between treatment groups and summarized along with the corresponding 95% CIs for treatment difference. In addition, summary statistics (mean change or mean % change) will be graphically presented as appropriate.

Binary Endpoints

For endpoints evaluating proportions, treatment comparisons will be performed using a stratified Cochran-Mantel-Haenszel test as appropriate with the randomization stratification factors as strata. Point estimates and 2-sided 95% CIs for treatment differences in proportions will be provided.

Descriptive statistics (point estimates and corresponding 95% CIs) will be provided by treatment group and visit as appropriate for all secondary endpoints.

Responder rate by visit (at Week 4, Week 8, Week 12, Week 16, and Week 20) will be derived in a similar fashion to the derivation of responder rate at Week 24/EOT. The missing data handling rules described in Section [7.3.5](#) for deriving responder status at Week 24/EOT will be applied similarly at Weeks 4, 8, 12, 16, and 20.

7.4.3. Derivation of Amenorrhea-Related Endpoints**Determination of Amenorrhea**

Rules for determining amenorrhea in the treatment period is defined as those who meet 1 of the following requirements for 2 consecutive visits (approximately 56 consecutive days). Patients will be deemed to have amenorrhea during a visit window according to the following rules:

- No feminine product returned due to reported amenorrhea in 2 consecutive visits

OR

- No feminine product returned due to other reasons or feminine product collection with a negligible observed MBL volume coupled with other data indicating infrequent non-cyclic bleeding/spotting as described in [Table 10](#).

Missing responses for menstrual bleeding questions in the eDiary will be treated as “No Bleeding” if eDiary compliance rate is > 70%.

Table 10: Rules for Determining Amenorrhea by Visit

Feminine Product Collection (KCAS) ^a	Supporting Data	
	Menstruation Status eCRF	eDiary
No feminine product collection due to reported amenorrhea	No menses start/stop dates reported	N/A
No feminine product collection due to other reasons	Per instructions for non-cyclic bleeding patterns, menses start date is reported but no menses stop date reported	
 • Data indicating infrequent, non-cyclic bleeding/spotting defined as bleeding/spotting with feminine product use for no more than 3 consecutive days and no more than 5 days bleeding total per visit window • eDiary entry rate > 70%
Feminine product collection with negligible observed MBL volume defined as <5 mL	Full or partial menses start and stop dates	
 • Data indicating infrequent, non-cyclic bleeding/spotting defined as bleeding/spotting with feminine product use for no more than 3 consecutive days and no more than 5 days bleeding total per visit window • eDiary entry rate > 70%

Abbreviations: eCRF, electronic case report form; eDiary, electronic diary; MBL, menstrual blood loss; N/A = not applicable.

^a There is no requirement for feminine product return rate, as the determination of amenorrhea is based on the eDiary response.

Amenorrhea During the Last 35 Days of Treatment

Patients with amenorrhea over the last 35 days of treatment are defined as those who meet the definition of amenorrhea. A patient's amenorrhea status will also be summarized at Weeks 8, 12, 16, and 20. If a patient does not return for her Week 24/EOT visit, the eDiary responses for the last 35 days of treatment will be evaluated. If the criteria for infrequent, non-cyclic bleeding or spotting as indicated in [Table 10](#) is met and the criteria for amenorrhea is met at the prior visit, the patient will be categorized as amenorrheic at Week 24/EOT. At all other timepoints, patients who do not return for a specific visit will be assigned as not amenorrheic at that visit.

Time to Amenorrhea

Time to amenorrhea is defined as the weeks from date of first dose of study drug to the start date of the amenorrhea window. Time to sustained amenorrhea will also be estimated and plotted using the Kaplan-Meier method.

The start date of amenorrhea is defined as the last feminine product collection date prior to start of amenorrhea. For example, if a patient's feminine product was collected at her Week 4 visit and MBL volume for this cycle did not indicate amenorrhea, and the patient reported amenorrhea on Week 8 and 12 visits, then time to start amenorrhea will be defined as starting on the date of feminine product collection for Week 4. Patients who are determined to have amenorrhea at Week 4 and Week 8 will use their Week 4 feminine product collection date as start date of amenorrhea. Patients without an event will be censored at the last assessment date prior to the last dose of the study drug.

Sustained Amenorrhea Rate by Visit

A patient's sustained amenorrhea status will be summarized at Weeks 8, 12, 16, 20, and 24, based on her time to achieving and maintaining amenorrhea until the date of last study drug dose as shown in [Table 11](#). For example, at Week 8, a patient is considered to have achieved sustained amenorrhea status if her amenorrhea started before Week 8 and was observed every visit thereafter until the last dose of the study treatment. The proportion of patients with sustained amenorrhea will be summarized by visit. If a patient met the criteria for sustained amenorrhea but discontinues from the study, this subject's amenorrhea status will be carried forward to the Week 24 visit.

Table 11: Sustained Amenorrhea Rate by Visit

Time Point	Amenorrhea Window	
	Start	End
Week 8	Determined amenorrhea at Week 4	Amenorrhea observed at Week 8 and was observed at every visit thereafter until and including the last dose of study treatment
Week 12	Determined amenorrhea at Week 8	Amenorrhea observed at Week 12 and was observed at every visit thereafter until and including the last dose of study treatment
Week 16	Determined amenorrhea at Week 12	Amenorrhea observed at Week 16 and was observed at every visit thereafter until and including the last dose of study treatment
Week 20	Determined amenorrhea at Week 16	Amenorrhea observed at Week 20 and was observed at every visit thereafter until and including the last dose of study treatment
Week 24	Determined amenorrhea at Week 20	Amenorrhea observed at Week 24

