7.3.5. Derivation of Responder Status at Week 24/EOT and Missing Data Handling Rules

For the evaluation of primary endpoint, missing data handling rules will be implemented for deriving responder status at Week 24/EOT as described below. The following elements will be checked: duration of treatment exposure; compliance with feminine product collection against the eDiary, as measured by FP RR; compliance with eDiary entry, defined as the proportion of eDiary entry days over the length (days) of FP collection interval for Week 24/EOT visit; and reasons for no FP collection (as displayed in [Table 7](#)).

Patients with < 4 weeks of treatment who withdraw from the study prematurely due to lack of efficacy or withdraw from the study prematurely to undergo surgical intervention for uterine fibroids will be considered as non-responders.

All other patients will have their responder status determined as follows:

- For patients with a FP RR of 100%, responder status will be determined based on the observed MBL volume;
- For patients who had incomplete feminine product collection, with a FP RR of < 100%, responder status will be derived based on either imputed or observed MBL volume;
 - Those with an MBL volume \geq 80 mL or < 50% reduction from Baseline will be considered as non-responders;
 - Those with an MBL volume < 80 mL and \geq 50% reduction from Baseline will be imputed for partial or complete missing MBL volume (see Section [7.3.6](#) for details).
- For patients who did not return a feminine product collection, responder status will be determined depending on the reason reported on the Feminine Product Collection eCRF:
 - If the reason is reported as Amenorrhea, the last 35 days of treatment will be used to derive responder status:
 - If the Week 24/EOT interval was 35 days, then she will be considered as a responder;
 - If the Week 24/EOT interval was <35 days, the following supportive information will be used to derive responder status:
 - If a patient reported amenorrhea at the visit prior to Week 24/EOT, she will be defined as a responder;
 - If a patient did not report amenorrhea at the visit prior to Week 24/EOT, eDiary data from the prior visit interval will be reviewed to confirm whether the patient was amenorrheic for a total of 35 days.

- If the eDiary from the previous interval confirms amenorrhea, then the patient will be considered as a responder;
- Otherwise, MBL volume will be imputed.

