7.4.1. Key Secondary Efficacy Endpoints with Alpha-Protection

For testing whether relugolix + E2/NETA (Group A) is statistically significantly superior to placebo (Group C) for the primary efficacy endpoint as well as the seven key secondary endpoints listed below, a gate-keeping mixed sequence testing procedure will be applied to maintain the family-wise type I error rate. Under this testing procedure, the primary endpoint

Statistical Analysis Plan

[figure not shown]
Amendment 1: Effective June 14, 2019

MVT-601-3001 and 3002

[figure not shown]
will be tested first at a 2-sided 0.05 significance level. If the p-value for primary endpoint is < 0.05 , the seven key endpoints listed below will be tested sequentially in the order depicted in [Figure 3 \(LIBERTY 1\)](#) and [Figure 4 \(LIBERTY 2\)](#).

For the relugolix + E2/NETA group to be considered statistically superior to the placebo group on a secondary endpoint, the two-sided p-value must be < 0.05 for that secondary endpoint and for all higher-ranking secondary endpoints, as well as for the primary endpoint. If the two-sided p-value is < 0.05 for the fourth endpoint (proportion of women with hemoglobin ≤ 10.5 g/dL at Baseline who achieve an increase of > 2 g/dL from Baseline at Week 24 for LIBERTY 1; proportion of women who achieve a maximum NRS score ≤ 1 for uterine fibroid-associated pain over the last 35 days of treatment in the subset of women with a maximum pain score ≥ 4 during the 35 days prior to randomization for LIBERTY2), the remaining three endpoints (the fifth, sixth, or seventh) will be tested using the Hochberg step-up procedure.

Figure 3: Mixed Sequence Testing Procedure for Primary and Key Secondary Endpoints in LIBERTY 1

Abbreviations: BPD = Bleeding and Pelvic Discomfort; EP = endpoint; Hgb = hemoglobin; max = maximum; MBL = menstrual blood loss; M-vol = myoma volume; NRS = Numerical Rating Scale; PE = primary endpoint; Prop = proportion; UFS-QoL BPD = Uterine Fibroid Symptom and Health-Related Quality of Life Bleeding and Pelvic Discomfort; U-vol = uterine volume.

Figure 4: Mixed Sequence Testing Procedure for Primary and Key Secondary Endpoints in LIBERTY 2

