Abbreviations: BPD = Bleeding and Pelvic Discomfort; EP = endpoint; Hgb = hemoglobin; max = maximum; MBL = menstrual blood loss; M-vol = myoma volume; NRS = Numerical Rating Scale; PE = primary endpoint; Prop = proportion; UFS-QoL BPD = Uterine Fibroid Symptom and Health-Related Quality of Life Bleeding and Pelvic Discomfort; U-vol = uterine volume.

From the Hochberg procedure, the p-values will be calculated for the three endpoints (5, 6, and 7) and ranked from the smallest to the largest. The endpoint corresponding to the largest p-value gets tested first. If the p-value is < 0.05 , then no further testing will occur, and it will be concluded that all three endpoints are positive. Otherwise, the endpoint corresponding to the second largest p-value will be tested. If the p-value is < 0.025 , then no further testing will occur, and it will be concluded that the endpoints corresponding to the middle and smallest p-values are positive. Otherwise, the endpoint with the smallest p-value will be tested. If the p-value is < 0.0167 , no further testing will occur, and it will be concluded that only the endpoint with the smallest p-value is positive. Otherwise, all three endpoints did not pass the statistical significance criterion at 0.05 level.

The seven key secondary efficacy endpoints are as follows:

1. Proportion of women who achieve amenorrhea over the last 35 days of treatment;
2. Percent change from Baseline to Week 24 in MBL volume;

- 3. *Change from Baseline to Week 24 in Bleeding and Pelvic Discomfort Scale score as measured by the UFS-QoL Symptom Severity Scale (Q1, Q2, Q5);*
- 4. *Proportion of women with a hemoglobin ≤ 10.5 g/dL at Baseline who achieve an increase of > 2 g/dL from Baseline at Week 24*
- 5. *Proportion of women who achieve a maximum NRS score ≤ 1 for uterine fibroid associated pain over the last 35 days of treatment in the subset of women with a maximum pain score ≥ 4 during the 35 days prior to randomization;*
- 6. Percent change from Baseline to Week 24 in uterine fibroid volume;
- 7. Percent change from Baseline to Week 24 in uterine volume.

For key secondary efficacy endpoints (1, 4, and 5) that are evaluating proportions, treatment comparisons will be performed using a stratified Cochran-Mantel-Haenszel test with the randomization stratification factors as strata. Point estimates and 2-sided 95% CIs for treatment differences in proportions will be provided.

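### The first-listed alpha-protected secondary is named for the last 35 days of treatment but is derived from two consecutive visits, about 56 days at nominal spacing

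*SAP*

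**What the plan says.** Table 1, Section 7.4.1 and Appendix 1 all name the endpoint by the last 35 days. In the Section 7.4.1 list of seven it is item 1: "Proportion of women who achieve amenorrhea over the last 35 days of treatment". It is alpha-protected. Once the primary passes, a claim requires that "the two-sided p-value must be < 0.05 for that secondary endpoint and for all higher-ranking secondary endpoints".

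Section 7.4.3 then defines amenorrhea generally. The opening sentence asks for one of the requirements to be met "for 2 consecutive visits (approximately 56 consecutive days"), and the first route repeats this: "No feminine product returned due to reported amenorrhea in 2 consecutive visits". The only link from the 35-day endpoint to a rule is this sentence: "Patients with amenorrhea over the last 35 days of treatment are defined as those who meet the definition of amenorrhea". A 35-day look-back appears only when the Week 24/EOT visit is missed. In that case "the eDiary responses for the last 35 days of treatment will be evaluated", and amenorrhea at the prior visit is also needed.

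The primary endpoint treats amenorrhea differently. Under Section 7.3.3, a woman who returned no product over the last 35 days and reported amenorrhea counts as amenorrheic with a volume of 0 mL. Under Section 7.3.5, a 35-day final interval is enough by itself to make her a responder. If the final interval is shorter, amenorrhea reported at the prior visit suffices; failing that, "eDiary data from the prior visit interval will be reviewed to confirm whether the patient was amenorrheic for a total of 35 days".

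**The concern.** The name and the derivation describe different quantities. A reader of the study report would take the rate as the share of women amenorrheic in the last 35 days, whereas the program would deliver the share meeting the criteria at the last two visits. The endpoint stands first in the listed hierarchy and supports a claim, so the estimate should be what its name says.

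There are three further effects:

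- For women who complete treatment, Table 11 defines sustained amenorrhea at Week 24 as amenorrhea at Weeks 20 and 24. Under the two-visit rule the gated endpoint becomes nearly the same as that separately listed, ungated one.
- Section 9.3.6 reuses the Section 7.4.3 definition for bleeding pattern. A woman with no bleeding days in her Week 24/EOT window who fails the two-visit rule cannot be cyclic, because that needs at least 3 days, so she falls by default into irregular bleeding.
- Section 7.4.3 does not say clearly which routes need two visits. Its opening sentence applies the requirement to all of them and the first route repeats it, but the second route and Table 10 work per visit window. Table 11 uses amenorrhea determined at Week 4, when only one post-Baseline visit is scheduled. Two programmers could derive different rates.

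**Working it through.** **Inputs.** Table 2 gives target days 29, 57, 85, 113, 141 and 169, with windows of Days 100–127 for Week 16, 128–155 for Week 20 and 156–196 for Week 24. Section 7.4.3 gives two visits, about 56 days. The endpoint name gives 35 days.

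**1. Reproduce the SAP's figure.** Successive targets are 28 days apart. Two intervals ending at Week 24 start after the Week 16 visit on Day 113, so they run from Day 114 to Day 169: 169 − 113 = 56 days. The stated figure is right.

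**2. The named period.** Thirty-five days ending on Day 169 start on Day 169 − 34 = 135.

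**3. The gap.** Days 114 to 134 are 56 − 35 = 21 days that the rule examines and the name does not (56/35 = 1.6).

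**4. Who is misclassified.** Table 10 tolerates infrequent bleeding or spotting with product use (at most 3 consecutive days and 5 days in total per window, with diary entry above 70%). With the same diary conditions it also tolerates returned product below 5 mL. The affected woman therefore meets the criteria over Days 135–169 and exceeded that allowance on Days 114–134.

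**5. Direct conflict with the primary.** Suppose her Week 20 visit was on Day 134, which is inside the Week 20 window. Her final interval is then 169 − 134 = 35 days. If she reports amenorrhea and returns no product:

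- Sections 7.3.3 and 7.3.5: amenorrheic, 0 mL, responder.
- Section 7.4.3: not amenorrheic, because the preceding interval fails.

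**6. Does a visit count secure 35 days?** At the extremes of the Table 2 windows, the time from the Week 16 visit to the Week 24 visit ranges from 156 − 127 = 29 days to 196 − 100 = 96 days. Two visits can thus cover less than 35 days or far more.

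**7. Size (illustration only).** The SAP gives no amenorrhea rates. Assume 35-day rates of 50% v 5%, 50% v 10% or 40% v 5%. Assume also that the longer rule removes 5 to 15 points in the active arm and the same share in placebo. The difference then falls, for example, from 40 to 36 points (50% v 10%, 5 points lost) or from 45 to 31.5 points (50% v 5%, 15 points lost). Across all the cases the fall is about 4 to 13.5 points. Power with 130 per arm stays above 99.9% (lowest value 0.9995).

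**The case against.** The two-visit rule looks deliberate. One nominal 28-day interval cannot cover 35 days, by-visit status starts at Week 8 (the first visit with two intervals), and Section 7.4.3 expressly maps the 35-day endpoint to the general definition. The rule is prespecified, applies equally to both arms and is stricter at nominal spacing. The primary is a blood-volume endpoint that uses reported amenorrhea to settle a missing volume, so a primary responder who is not amenorrheic is no contradiction in itself. When the final interval is under 35 days and the prior visit also reported amenorrhea, the two derivations largely agree.

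Most of this stands, and it limits the point. It does not remove the mismatch: the need for data from a second interval to reach 35 days is no reason to require the criteria throughout that interval. Section 7.3.5 shows how to stop at a total of 35 days, and the missed-visit rule in Section 7.4.3 shows that the diary can be read that way.

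A reader might infer more than the SAP supports:

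- *That 56 bleeding-free days are required.* They are not, because Table 10 allows limited bleeding or spotting in each window.
- *That women who stop early can never qualify.* A woman who stops after Week 4 and attends an EOT visit has a second visit, and the missed-visit route may admit others. Many very early stoppers have under 35 days of treatment and could not show 35-day amenorrhea under any rule.
- *That error control or the gate is compromised.* Nothing in the SAP shows this.

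**Conclusion.** The mismatch is real and stands in the current text: an alpha-protected endpoint is named for 35 days and derived from two visits. At nominal spacing the look-back is 21 days longer than named, which lowers the reported rate in both arms. How many women are affected is unknown, and the point differences above rest wholly on assumed rates. Away from nominal spacing the look-back may be shorter or longer than 35 days, so the direction is not guaranteed for every woman.

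The direct conflict with the primary is narrow: a 35-day amenorrheic final interval preceded by more bleeding than Table 10 allows. What is at stake is the meaning and size of the reported estimate. Sample size is not affected.

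**What to change.** Choose one of the following before unblinding.

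- **Keep the name.** Give the Week 24/EOT endpoint its own rule: Table 10 criteria in the Week 24/EOT window, with earlier data used only to reach a total of 35 days, as in Section 7.3.5. Keep the two-visit rule for sustained and by-visit amenorrhea. Table 10 lists no diary requirement for the reported-amenorrhea route, so state that the diary is used there when the final interval is under 35 days. At nominal spacing this option shortens the duration required for a gated endpoint, so the reason should be recorded.
- **Keep the rule.** Rename the endpoint in Table 1, Section 7.4.1, Section 7.4.3 and Appendix 1 as amenorrhea at the last two consecutive visits.

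In either case, state whether the two-visit requirement applies to every Table 10 route.

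The first option costs SAP wording and a small change to the derivation program. Renaming costs wording only. Neither needs new data.

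### SAP 7.4.3: the Week 8 example and Table 11 differ by one visit on when sustained amenorrhea counts, and women amenorrheic from Week 4 are dated by a different rule from all others

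*SAP*

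**What the plan says.** All the rules are in SAP 7.4.3.

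- **Amenorrhea.** A woman must "meet 1 of the following requirements for 2 consecutive visits (approximately 56 consecutive days").
- **Time-to-event definition.** "Time to amenorrhea is defined as the weeks from date of first dose of study drug to the start date of the amenorrhea window".
- **General start-date rule.** "The start date of amenorrhea is defined as the last feminine product collection date prior to start of amenorrhea". In the worked example, product collected at Week 4 does not indicate amenorrhea and amenorrhea is reported at Weeks 8 and 12; "then time to start amenorrhea will be defined as starting on the date of feminine product collection for Week 4".
- **Special case.** "Patients who are determined to have amenorrhea at Week 4 and Week 8 will use their Week 4 feminine product collection date as start date".
- **Sustained amenorrhea by visit.** Status rests on the time to achieving and maintaining amenorrhea, with a reference to Table 11. The Week 8 illustration is that "a patient is considered to have achieved sustained amenorrhea status if her amenorrhea started before Week 8 and was observed every visit thereafter", to the last dose.
- **Table 11.** The window start in the Week 8 row is "Determined amenorrhea at Week 4" and in the Week 12 row "Determined amenorrhea at Week 8"; the later rows follow the same pattern.

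Appendix 1 assigns a Cochran-Mantel-Haenszel test to the sustained rate (monthly) and log-rank tests with Kaplan-Meier summaries to time to amenorrhea and time to sustained amenorrhea. The same wording stands in Amendment 1 and in the SAP that it amended.

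**The concern.** The sentence meant to illustrate Table 11 gives a different answer from Table 11 for any woman whose sustained run begins at Week 8, 12, 16 or 20. A programmer who derives sustained status from the start date and one who codes Table 11 would report different rates at Weeks 8 to 20, and so different Cochran-Mantel-Haenszel results. Those are the visits that describe how early the effect appears.

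The second problem is in the start date itself. For most women it marks the opening of their first amenorrheic window. For women amenorrheic at both Week 4 and Week 8 it marks the close of that window. The women with the earliest onset therefore become tied events with women who bled until Week 4, on both Kaplan-Meier curves, and the SAP gives no reason.

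The term for the amenorrhea window adds to the difficulty. It appears in the time-to-event definition and as the column heading of Table 11, with different meanings.

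**Working it through.** The SAP states no figure to reproduce here. The check traces bleeding patterns through both rules.

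**Inputs.** Visits at Weeks 4, 8, 12, 16, 20 and 24; the rules quoted above; the Table 5 windows (the Week 4 window opens on Study Day 1 and closes at the Week 4 collection X1; the Week 8 window opens at X1 + 1); the Week 4 target day of 29 (Table 2). Where no product is returned because of amenorrhea, Table 5 uses the visit date, so a Week 4 date always exists. The women traced attend all six visits.

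**Rules as formulas.** Let v be the first visit of an unbroken amenorrheic run to Week 24, of at least two visits.

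- Start date by the SAP: S = v − 4 for v ≥ 8; S = 4 for v = 4 (special case).
- Text: sustained at week w if S < w and amenorrhea is observed at w and at every later visit.
- Table 11: sustained at w if amenorrhea is present at w − 4, at w and at every later visit. The first week counted is therefore v + 4.

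| First amenorrheic visit v | SAP start S | First week counted, text | First week counted, Table 11 |
|---|---|---|---|
| 4 | 4 | 8 | 8 |
| 8 | 4 | 8 | 12 |
| 12 | 8 | 12 | 16 |
| 16 | 12 | 16 | 20 |
| 20 | 16 | 20 | 24 |

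**All patterns.** Over the 2^6 = 64 possible patterns, the rules disagree for 1, 2, 4 and 8 patterns at Weeks 8, 12, 16 and 20, and for none at Week 24. The disagreeing patterns at week w are those with no amenorrhea at w − 4 and amenorrhea from w on. Visits before w − 4 are free, which gives 2^0, 2^1, 2^2 and 2^3. At Week 24 such a run has a single visit and fails the two-visit definition.

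**Size.** At each of Weeks 8 to 20, text rate − Table 11 rate = share of women whose sustained run begins at that visit. The shift in the difference between arms is the difference between the arms' shares. The SAP gives no shares. For illustration only, with assumed shares of onset at Weeks 4/8/12/16/20:

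| Assumed shares (%) | Week 8, text | Week 8, Table 11 | Gap (points) |
|---|---|---|---|
| 10/10/10/10/10 | 10 + 10 = 20% | 10% | 10 |
| 5/25/10/5/5 | 5 + 25 = 30% | 5% | 25 |
| 25/15/5/5/2 | 25 + 15 = 40% | 25% | 15 |

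**Start dates.** A woman with v = 8 starts at X1, where her first amenorrheic window opens. A woman with v = 4 also starts at X1, where hers closes. Taken literally, the general rule would send the second woman to a pre-treatment collection, at or before first dose, so time 0 if bounded there. On target days the difference is 29 − 1 = 28 days, or 4 weeks.

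**The case against.** The strongest reply is that Table 11 already governs. The text refers to it, the Week 8 sentence is only an example, and the two-consecutive-visit definition fits the table: a woman who met the criteria only at Week 8 has not yet had two visits. This settles which rule to keep. It does not remove the conflict. Sustained status is tied in the text to the time of achieving amenorrhea, the SAP's own worked example puts that time at Week 4, and the status is retrospective in any case because it depends on all later visits.

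The reply on dating also has force. The Week 4 rule is explicit, two programmers would apply it alike, and some special case is needed because the general rule points before treatment. A bleed-free first window does not prove that amenorrhea began on Day 1, since 7.3.3 gives natural intervals of about 21 to 35 days. A reader might infer that these onsets are shown to be 4 weeks late. The documents support only an unexplained departure from the general rule, of up to about 4 weeks.

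It is also true that aligning the rules still leaves a Week 8 onset at about Week 4 on the curve and at Week 12 in Table 11. That is the difference between onset and confirmation, and it is acceptable once stated.

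**Conclusion.** The inconsistency holds. For onset at the Week 8, 12, 16 or 20 visit, the text counts a woman as sustained one visit earlier than Table 11, so at Weeks 8 to 20 the text rate is never the lower one. The rules agree for Week 4 onset and for the Week 24 rate, the latter because of the two-visit definition. The direction is certain. The size is not: it depends on onset shares that the SAP does not give, and the gaps of 10 to 25 points at Week 8 are illustrations from assumed shares.

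Separately, women amenorrheic at Weeks 4 and 8 are dated by a different convention from everyone else and tie with women who bled until Week 4.

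A reader might go further and conclude that the planned rates and curves are wrong, or that a protected claim is at risk. The documents do not support either. Which rule was intended is not stated. These are other secondary endpoints whose p-values are nominal under SAP 7.2, and the gate-kept endpoint, amenorrhea over the last 35 days, does not use the start-date or sustained rules. The point is worth correcting because it is cheap and because choosing after unblinding would mean choosing between two sets of early results.

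**What to change.** Before unblinding:

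1. State that Table 11 governs sustained status, in line with the two-consecutive-visit definition. Rewrite the Week 8 example as amenorrhea determined at Week 4, observed at Week 8 and at every later visit to the last dose.
2. Define onset once, as the start of the first Table 5 window in the unbroken amenorrheic run, with the date of first dose when that is the Week 4 window. This replaces the Week 4/Week 8 special case. If the Week 4 date is a deliberate convention, say so and show first-dose dating as a sensitivity analysis.
3. State that the Kaplan-Meier curve shows onset and that Table 11 shows confirmed status.

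The cost is a wording change and one derivation. Sustained rates at the early visits will be lower than under the text reading wherever any woman's sustained run begins at that visit. First-dose dating, if adopted, moves the earliest events on the curves to time zero.
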